## 2.- Postoperative intravenous fluid balance

Following surgery, participants will be hospitalized for 24 hours. During the postoperative period, the investigators will keep track and document the exact volume of fluid administered in milliliters.

## Secondary Outcome Measures

### 3.- The intraoperative total volume of urine in the participant's catheter bag

During the intraoperative period, the investigators will measure and record the total volume of urine accumulated in the participant's catheter bag over the surgery period and will report urine output measured in milliliters per kilogram per hour.

### 4.- The postoperative total volume of urine in the participant's catheter bag

During the postoperative period, the investigators will measure and record the total volume of urine accumulated in the participant's catheter bag over a 24-hour period and will report urine output measured in milliliters per kilogram per hour.

### 5.- Mean arterial blood pressure during hospitalization

Following surgery, participants will be hospitalized for 24 hours. During this time, the investigators will monitor mean arterial pressure.

### 6.- The intraoperative intravenous fluid balance

Throughout the surgical procedure, the investigators will meticulously monitor and record the precise amount of fluid administered in milliliters.

## **Eligibility**

### Inclusion Criteria

- Female patients between 21 and 60 years old
- Liposuction with or without abdominoplasty
- American Society of Anesthesiologists I & II.

### Exclusion Criteria

- History of previous liposuction surgery
- American Society of Anesthesiologist III

- Coagulation disorders
- Cardiopulmonary disorders

## Statistical analysis

We will express continuous variables as means with standard deviation and percentages for categorical variables. To test the data statistically, we will use Student's t-test or Chi-square test depending on the appropriateness. P-values less than 0.05 will be considered statistically significant. The analyses and calculations will be performed using SPSS Statistics 21.0 (IBM, NY, USA).

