## Study Description

The research will involve 50 female patients who have undergone liposuction and will be divided into two groups.

**Group Intraoperative fluid ratio:** Fluid administration will be determined by the intraoperative fluid ratio. This ratio is calculated by dividing the sum of subcutaneous infiltration and intravenous fluid by the total aspirate volume. Depending on the aspiration volume, it will be maintained at 1-1.4.

**Group Carotid Artery Peak Velocity Variation:** Participants will be given a fluid maintenance rate of 1.5 ml/kg/h. To determine fluid responsiveness, the carotid artery peak velocity variation ( $\Delta V_{Peak-CA}$ ) will be measured before, during, and after the procedure. If the  $\Delta V_{Peak-CA}$  goes above 15%, the patient will receive a fluid bolus of lactated ringer solution at a rate of 4-6 ml/kg over 10-15 minutes, and the team will re-measure fluid responsiveness 10 minutes after each  $\Delta V_{Peak-CA}$ .

During the examination, a single cardiothoracic anesthesiologist will use a 13-6 MHz linear probe (Fujifilm Sonosite M-Turbo) to measure the peak velocity of the carotid artery on the left side. The sample volume will be positioned at the center of the lumen, 2 cm from the bulb, and a pulsed wave Doppler examination will be conducted.

To measure the  $\Delta V_{Peak-CA}$ , the investigators will calculate the maximum and minimum values during one respiratory cycle. This will be done by using the formula:  $100 \times (\text{maximum peak velocity} - \text{minimum peak velocity}) / [(\text{maximum peak velocity} + \text{minimum peak velocity})/2]$ .

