## Surgical technique

The superwet tumescence technique will be the only method utilized for infiltration during the procedure. All participants will undergo power-assisted liposuction, and a single surgeon will operate. The wetting solution will contain 1000cc of normal saline and 2mg of epinephrine in a 1:500,000 ratio. The total infiltration volume will depend on the participant's surgery characteristics. The total amount of aspiration will depend on the participant and surgery plan and can vary between 2500 to 5000 ml

During the surgical procedure, the investigators will monitor vital signs such as blood pressure, heart rate, temperature, oxygen levels, and urine output. Additionally, the investigators will track the amount of fluids given and removed and the volume of blood aspirated.

Following surgery, participants will be hospitalized for 24 hours. During this time, the investigators will closely monitor the plethysmography variability index (PVi) in both groups.

If the PVi exceeds 15%, patients will receive a ringer lactate fluid bolus of 4-6 ml/kg over 10-15 minutes. Additionally, the investigators will keep track of their urine output, total fluid balance, and vital signs

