## **Arms and interventions**

Experimental: Group Carotid Artery Peak Velocity Variation

Participants will be given a fluid maintenance rate of 1.5 ml/kg/h. To determine fluid responsiveness, the carotid artery peak velocity variation ( $\Delta V_{Peak-CA}$ ) will be measured before, during, and after the procedure. If the  $\Delta V_{Peak-CA}$  goes above 15%, the participant will receive a fluid bolus of lactated ringer solution at a rate of 4-6 ml/kg over 10-15 minutes, and the team will re-measure fluid responsiveness 10 minutes after each  $\Delta V_{Peak-CA}$ .

Active Comparator: Group Intraoperative fluid ratio

The intraoperative fluid ratio will determine fluid administration. This ratio is calculated by dividing the sum of subcutaneous infiltration and intravenous fluid by the total aspirate volume. Depending on the aspiration volume, it will be maintained at 1-1.4.

This ratio is calculated by dividing the sum of procedure subcutaneous infiltration and intravenous fluid by the total aspirate volume during surgery

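### Student's t-test is the only test named for continuous outcomes, although equal group sizes are not fixed and equal spread cannot be assumed; naming Welch's test is a minor, low-cost improvement

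*Combined protocol and SAP*

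**What the plan says.** The Statistical analysis section gives one sentence on tests: "we will use Student's t-test or Chi-square test depending on the appropriateness". The decision rule is "P-values less than 0.05 will be considered statistically significant", and the software is SPSS 21.0. The section does not say whether variances are pooled, names no unequal-variance version, and gives no rule for arms that differ in spread. All six outcomes under Outcome Measures are continuous, so the t-test governs every one of them.

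On group sizes, the Study Description says: "The research will involve 50 female patients who have undergone liposuction and will be divided into two groups". No section gives a number per arm, an allocation ratio or a method of allocation.

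On fluid during surgery, Arms and interventions gives two rules. For the fluid-ratio arm: "Depending on the aspiration volume, it will be maintained at 1-1.4". For the carotid arm: "Participants will be given a fluid maintenance rate of 1.5 ml/kg/h", plus boluses triggered by the carotid index.

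After surgery, according to Surgical technique, "the investigators will closely monitor the plethysmography variability index (PVi) in both groups". One PVi-triggered bolus rule follows, with no distinction by arm. No standard deviation is given for any outcome.

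**The concern.** Student's test estimates one common variance, and the larger arm carries more weight in it. If the smaller arm is the more variable one, the standard error comes out too small and the test rejects too often. If the larger arm is more variable, the reverse happens. With equal arms the two effects nearly cancel.

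In one arm intraoperative fluid follows aspirate volume through a ratio. In the other it follows weight, time and a count of boluses. Nothing in the plan makes the spread of these two quantities equal, and nothing guarantees equal arms at analysis. At stake are the real error rate behind the plan's only decision rule and the standard error of every mean difference. Because SPSS prints both the pooled and the unequal-variance result, a plan that does not name one also leaves room to choose after seeing the data.

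**Working it through.** **Inputs.** Total N = 50 (Study Description). Alpha = 0.05 (Statistical analysis); sidedness is not stated, so two-sided is assumed. Split and SD ratio are not in the documents; the ranges shown are assumptions. Outcomes are taken as normal.

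**Step 1: the plan's own figure.** With equal SDs the pooled test gives 5.0% at every split, which matches the stated level. N = 50 itself cannot be reproduced, because no effect size, SD or power is given.

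**Step 2: how the pooled standard error goes wrong.** The true variance of the mean difference is s1²/n1 + s2²/n2. The pooled test targets [(n1−1)s1² + (n2−1)s2²]/(n1+n2−2) × (1/n1 + 1/n2). With SDs of 2 and 1:

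- 25/25: true 4/25 + 1/25 = 0.200; pooled 2.5 × 0.08 = 0.200. No distortion.
- 20/30, larger SD in the smaller arm: true 4/20 + 1/30 = 0.233; pooled (19×4 + 29)/48 × 0.0833 = 0.182. The standard error is √(0.182/0.233) = 0.88 of its true value.
- 20/30, larger SD in the larger arm: true 1/20 + 4/30 = 0.183; pooled (19 + 29×4)/48 × 0.0833 = 0.234. The standard error is √(0.234/0.183) = 1.13 of its true value.

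**Step 3: type I error at nominal 5%**, by numerical integration over the two sample variances:

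| Split | SD ratio | Pooled, larger SD in smaller arm | Pooled, larger SD in larger arm | Welch |
|---|---|---|---|---|
| 25/25 | 2 | 5.2% | 5.2% | 5.0% |
| 25/25 | 3 | 5.4% | 5.4% | 5.0% |
| 22/28 | 2 | 7.0% | 3.7% | 5.0% |
| 20/30 | 1.5 | 7.0% | 3.5% | 5.0% |
| 20/30 | 2 | 8.5% | 2.9% | 5.0% |
| 20/30 | 3 | 10.0% | 2.4% | 5.0% |

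At 25/25 the two pooled columns are the same by symmetry. Simulation of the 20/30, ratio 2 case gave 8.5% to 8.6% and 2.8%, which agrees within simulation error. Over all splits from 25/25 to 17/33 and SD ratios from 1/3 to 3, Welch's test stays between 4.98% and 5.04%.

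**Step 4: how likely an uneven split is.** Under simple 1:1 allocation (an assumption), Binomial(50, 0.5) gives 48% for 22/28 or worse and 20% for 20/30 or worse, counting both directions. Averaged over all splits, the pooled error is 5.1% to 5.2% at SD ratio 1.5, 5.4% at ratio 2 and 5.8% at ratio 3.

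**Step 5: the price of Welch when SDs are equal.** Power at a standardised difference of 0.8, pooled against Welch: 79.1% and 79.1% at 25/25 (the gap is below 0.1 point); 77.5% and 77.1% at 20/30; 75.8% and 75.1% at 18/32.

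**The case against.** The strongest reply is that the pooled test may do no harm here. The natural reading of 50 patients in two groups is 25 and 25, where the error hardly moves. Even under simple allocation the conservative and liberal splits largely cancel, and the inflating direction of a 20/30 or worse split has a probability of only about 10%. The text does not say that variances are pooled, and the named software prints the unequal-variance result anyway. All of this stands. It limits the size of the point but gives no reason to prefer the pooled test.

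Two stronger readings are tempting, and the documents support neither.

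- **That the spread of intraoperative fluid is known to differ.** A reader might fix the fluid ratio at one value and find a small spread in that arm. Take aspirate as uniform over the 2500 to 5000 ml given in Surgical technique (SD 2500/√12 = 722 ml) and infiltration as equal to aspirate, so that intravenous fluid is (ratio − 1) × aspirate. A fixed ratio of 1.2 gives an SD of 0.2 × 722 = 144 ml. But the plan lets the ratio run from 1 to 1.4. If it is uniform over that range and independent of aspirate, the SD is √(0.05333 × 14,583,333 − 750²) = 464 ml. The answer depends on the assumption, so neither the size nor the direction of any inequality can be derived.
- **That the primary outcomes are affected.** Mean postoperative PVi and postoperative fluid are both measured under one bolus rule stated without distinction by arm. Unequal spread there is possible but not shown.

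**Conclusion.** The point holds as a minor improvement. The plan names only Student's test for six continuous outcomes, does not fix equal arms, and doses intraoperative fluid by different rules, so equal variance is an assumption that nothing in the plan supports. The direct bearing is on the secondary intraoperative outcomes.

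The error is visibly off 5% only when uneven arms and unequal SDs occur together: for example, a twofold SD ratio with a 22/28 or 20/30 split. Neither condition is given in the documents. A reader might conclude that the trial's 5% level has failed; the documents do not show that. What they show is that the plan relies on a condition it need not rely on, when a test that holds about 5% in every setting examined costs less than 1 point of power. These figures rest on normal outcomes and a two-sided test.

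**What to change.** In the Statistical analysis section, replace Student's t-test with Welch's unequal-variance t-test for all continuous outcomes, and state that each mean difference will be reported with its Welch 95% confidence interval. Name it before the data are seen, so that no choice between the two SPSS results remains and no preliminary test of equal variances is needed.

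Stating the planned number per arm would also help, but it does not replace the change, because drop-outs can still unbalance the arms.

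The cost is one line of text and no new software. If the variances turn out equal, the loss of power is below 0.1 point at 25/25, about 0.4 point at 20/30 and about 0.7 point at 18/32.

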## **Outcome Measures**

Primary Outcome

1.- Mean Postoperative PVi

Following surgery, participants will be hospitalized for 24 hours. Throughout this period, we will keep a close eye on the Plethysmography Variability Index in both groups. The PVi is a dynamic index that measures the relative variability of the plethysmography waveform detected noninvasively from a pulse oximetry sensor, ranging from 0 to 100. By automatically calculating the dynamic changes that occur during the respiratory cycle, it uses the detected amplitudes. A higher variability in the plethysmography waveform has been linked to preload dependence and fluid responders. If the PVi exceeds 15%, the patient will receive a fluid bolus of lactated ringer solution at a rate of 4-6 ml/kg over 10-15 minutes.

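### Postoperative IV fluid, the second primary, is recorded in ml although its boluses are dosed per kg; prespecified adjustment for weight and planned abdominoplasty is a cheap safeguard with a small, uncertain power gain

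*Combined protocol and SAP*

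**What the plan says.** - **Outcome.** "2.- Postoperative intravenous fluid balance" is the second item under the primary outcome heading, ahead of the secondary outcomes. Its text says the investigators will "document the exact volume of fluid administered in milliliters". The title names a balance; the description is of volume given.
- **Fluid rule after surgery.** Outcome Measures: "If the PVi exceeds 15%, the patient will receive a fluid bolus of lactated ringer solution at a rate of 4-6 ml/kg". Surgical technique gives the same trigger for both groups: "patients will receive a ringer lactate fluid bolus of 4-6 ml/kg over 10-15 minutes". No other fluid rule is set out for the 24-hour stay. The carotid group's own rule (Arms and interventions), which includes measurement after the procedure, is also dosed per kg.
- **Case mix.** Inclusion Criteria admit "Liposuction with or without abdominoplasty". No stratification by procedure is described.
- **Scaling elsewhere.** For postoperative urine the investigators "will report urine output measured in milliliters per kilogram per hour"; intraoperative urine is treated the same way.
- **Analysis.** The Statistical analysis section plans Student's "t-test or Chi-square test depending on the appropriateness" with significance at p below 0.05. It names no covariate, model or weight scaling.
- **Size and allocation.** "The research will involve 50 female patients who have undergone liposuction and will be divided into two groups" (Study Description). The documents state neither the allocation ratio nor the method of allocation.

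**The concern.** Two patients who trigger the same number of boluses receive different volumes in ml if their weights differ. The plan removes weight from urine output but leaves it in a primary outcome. Variation due to weight, and any due to procedure, then counts as noise in the t-test.

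With only 50 patients, a chance difference between the arms in weight or abdominoplasty share also stays in the estimated fluid difference. If such an imbalance appeared and the analysis were adjusted only then, the choice would look post hoc. At stake are some precision and the credibility of one primary result, not the validity of the test.

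**Working it through.** **Inputs.** From the documents: 50 patients, two groups, threshold 0.05, boluses of 4-6 ml/kg. Assumed: 25 per arm and a two-sided test. The documents give no power, effect size, SD, weights, bolus counts or abdominoplasty share, so there is no planned figure to reproduce; the values of these used below are assumptions.

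**1. How weight enters.** At 50 kg one bolus is 4 × 50 to 6 × 50 = 200-300 ml; at 90 kg it is 360-540 ml. The same number of boluses gives a ratio of 90/50 = 1.8 from weight alone.

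**2. Share of variance due to weight, boluses only.** Let volume = weight × S, where S sums a Poisson number of boluses (mean m), each uniform on 4-6 ml/kg (mean 5, mean square 25.33). With weight coefficient of variation cv:

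R² = cv²(5m)² / [(1 + cv²)(25.33m + 25m²) − 25m²]

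| m | cv | R² |
|---|---|---|
| 0.5 | 10% | 0.0625 / 12.86 = 0.5% |
| 2 | 15% | 2.25 / 54.06 = 4.2% |
| 4 | 20% | 16 / 121.4 = 13.2% |

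**3. Chance imbalance under random allocation.**
- Weight: the SE of the difference in means is √(2/25) = 0.283 SD. The chance of a difference of at least 0.4 SD is 16%. Such a difference shifts mean fluid by 0.4 × cv = 4-8% (cv 10-20%), or 0.4 × √R² / 0.283 = 0.10-0.51 standard errors.
- Abdominoplasty: the exact binomial chance of a gap of at least 20 points (5 of 25) is 11%, 16% or 20% for a share of 20%, 30% or 50%. If abdominoplasty changes fluid by 0-1.0 SD, a 20-point gap shifts the estimate by 0.20 × (0 to 1.0) / 0.283 = 0-0.71 standard errors.

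**4. Power of the adjusted model.** With 25 per arm the t-test has 80% power for a difference of 0.81 SD. Two baseline covariates multiply the variance by (1 − R²)(1 + 2/45) and leave 46 of 48 degrees of freedom. From the noncentral t:

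| Total R² | Power | Change (points) | Difference detectable at 80% |
|---|---|---|---|
| 0 | 78.2% | −1.8 | 0.83 SD |
| 5% | 80.2% | +0.2 | 0.81 SD |
| 10% | 82.3% | +2.3 | 0.78 SD |
| 20% | 86.5% | +6.5 | 0.74 SD |
| 30% | 90.5% | +10.5 | 0.69 SD |

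The variance factor equals 1 at R² = 1 − 45/47 = 4.3%. With the lost degrees of freedom, break-even is at about 5%.

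**5. Simulation of the bolus-only outcome** (20,000 trials per setting, mean weight 70 kg, m = 1, 2 or 4, cv 10-20%, no abdominoplasty effect). Power was 78.7-83.2% for the t-test on ml, 78.2-82.7% for the adjusted model and 81.4-84.8% for a t-test on ml/kg. Adjustment changed power by −1.7 to +2.5 points. In a separate run of nine settings (8,000 trials each), it beat the ml t-test in two, by at most 3.0 points (80.8% against 77.8%), and trailed the ml/kg t-test in all nine.

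**6. If the 24-hour total holds other fluid (assumed).** With 20 ml/kg of extra weight-based fluid in both arms, the ml t-test falls to 45-78% power and the adjusted model keeps 79-82%. With 2000 ml of extra fixed fluid, the ml/kg t-test falls to 32-80% and the adjusted model keeps 78-82%.

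**The case against.** The strongest case against is that, on the rule actually written down, adjustment hardly helps. The central value in step 2 (4.2%) lies below the 5% break-even, and a t-test on ml/kg does better in the bolus-only model. The large gains in step 6 need fluid that no section describes. A gain from abdominoplasty has a similar weakness: boluses follow only from PVi above 15%, so a higher bolus count after abdominoplasty presumes an effect on PVi that the documents do not state. Bolus totals may also contain many zeros, and their spread grows with weight. The outcome's title leaves open whether output is to be subtracted.

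Most of this stands, and it limits the point to a modest one. Three things remain. The downside is about 2 power points. Adjustment prespecified now deals with a chance imbalance without a later choice. The adjusted model also holds its power whether or not the fluid scales with weight, whereas each t-test loses power in one of the two cases in step 6. Zeros and uneven spread trouble the planned t-test on ml as well, so they are no reason to prefer it. If the outcome is a net balance, the figures in steps 2 and 5 no longer apply.

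A reader might infer that the t-test is wrong or biased. The documents do not support that if allocation is random; they say only that patients are divided, and without randomisation adjustment would matter more. A reader might also extend the point to mean PVi, but no section links PVi to weight or abdominoplasty.

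**Conclusion.** The point holds as an optional improvement of low severity. Weight enters a primary outcome by construction and the plan neither scales nor adjusts for it.

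The expected power change ranges from a loss of about 2 points to a gain of about 6 as total R² goes from 0 to 20%, and the documents do not say where in that range the trial lies. If the total is boluses only and abdominoplasty has no effect, the range is about −2 to +3 points. To claim a substantial power gain would be to rely on an abdominoplasty effect or on other weight-based fluid, neither of which the documents give.

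The firmer benefit is protection against chance imbalance: about a 16% chance of a weight gap of 0.4 SD or more, and 11-20% of a procedure gap of 20 points or more. All of this assumes 25 per arm, random allocation and an outcome read as volume administered.

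**What to change.** In the Statistical analysis section, prespecify the following:
- **Primary analysis of postoperative IV fluid:** a linear model for volume administered (ml) with arm, preoperative body weight and planned abdominoplasty (yes/no), reporting the adjusted difference with its 95% confidence interval.
- **Definition:** state that the outcome is volume administered, although its title says balance.
- **Sensitivity analysis:** the unadjusted t-test on ml.
- **Supporting result:** volume in ml/kg, in line with the urine outcomes. It is supporting only because it loses power if part of the fluid does not scale with weight.
- **Mean PVi:** keep the t-test.
- **Covariates to leave out:** actual aspirate, infiltration and intraoperative IV volumes, which are determined after allocation. Use planned, not performed, abdominoplasty for the same reason.

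**Cost.** A few sentences and one general linear model procedure in SPSS, the software already named. Weight is needed for per-kg dosing and abdominoplasty belongs to the surgical plan, so no extra patients, visits or data are required. The model uses two of 48 degrees of freedom and loses about 2 power points if neither covariate is prognostic. Labelling one analysis as primary keeps the additional results from becoming extra confirmatory tests.
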